7.1 Interim Analyses

Interim analyses will be performed. Blinded PK, safety and tolerability data will be reviewed after each cohort for dose selection. Details are given in the Interim Review Plan and in the safety Review Group Charter signed at the beginning of the study.

An additional interim analysis (including interim database lock) will be performed after Cohorts 1 and 2 have completed and unblinded, to evaluate the progression into later phase studies.

7.2 Final Analysis

This study will have one database, however Cohorts 1 and 2 will be analysed and reported separately from Cohort 3. Each cohort (Cohorts 1 and 2) and (Cohort 3) will be locked once all subjects have completed, data have been entered, all queries resolved and protocol deviations identified for that cohort of the study. Each cohort (Cohorts 1 and 2) and (Cohort 3) of the study will be unblinded following database lock. Final analyses will be carried out following database lock and unblinding for each cohort (Cohorts 1 and 2) and (Cohort 3) of the study.

8.1 Sample Size Assumptions

No formal statistical sample size estimation has been performed, due to the exploratory nature of this study. 6 subjects per dose level (cohort) is considered sufficient to examine the safety and tolerability of emodepside, as well as the pharmacokinetics after single and multiple doses.

9 Analysis Populations

The following populations will be identified:

Safety Population: All subjects who received at least one dose of IMP.

PK Concentration Population: All subjects who received at least one dose of IMP and for whom a pharmacokinetic sample was analysed.

PK Parameter Population: All subjects in the PK Concentration Population for whom pharmacokinetic parameters can be derived.

In all populations, treatment will be assigned based upon the treatment subjects actually receive regardless of the treatment to which they were randomised.

The primary endpoint will be analysed using the safety population.

9.1 Analysis Datasets

All analysis datasets will be based on observed data, except as outlined in Section 12.2.

10 Treatment Comparisons

The treatment comparison of interest is active (emodepside) versus placebo.

11 General Considerations for Data Analyses

11.1 Data Display Treatment and Other Subgroup Descriptors

The sort order for treatment groups will be placebo, then study treatment in ascending dose order. When a total column is included, it immediately follows the treatment groups which it aggregates.

Listings of data will be sorted and displayed by treatment group, subject number, and also by date and time if applicable.

The treatment descriptions to be used on all tables and listings are:

Treatment Groups	Short Description
Placebo [OD or BID]	PLA [OD or BID]
Emodepside xx mg [OD or BID]	xx mg [OD or BID]

11.2 Conventions for Summary Statistics and Data Displays

The minimum set of summary statistics for numeric variables will be: n, mean, standard deviation (or standard error), median, minimum, and maximum. 95% confidence intervals will be presented where appropriate for data interpretation.

Categorical data will be summarised in frequency tables with n and percentage. Summaries of a categorical variable will include all recorded values.

The minimum and maximum values will be presented with the same number of decimal places as the raw data collected on the CRF (or to 3 significant figures for derived parameters less than 100 and as integers for values more than 99). The mean and percentiles (e.g. median, Q1, and Q3) will be presented using one additional decimal place. The standard deviation and standard error will be presented using two additional decimal places.

12 Data Handling Conventions

12.1 Premature Withdrawal and Missing Data

All subjects who withdraw prematurely from the study or study drug will be included in the statistical analyses.

If a subject completes the treatment period but has missing data, then this will be made apparent in the subject listings. Missing data will not be imputed except for as outlined in Section 12.2.

If the study is prematurely discontinued, all available data will be listed and a review will be carried out to assess which statistical analyses are still considered appropriate.

Data collected at unscheduled time points during the study will not be used in the summaries or data analyses. They will be included in the listings.

If time information (i.e. hours and/or minutes) for adverse events or concomitant medication is missing, but the day is present, then the time will be calculated in days. If date information is partial or missing, then any derived times (e.g. AE start time from last study medication) will be listed as missing.

Conventions for handling missing plasma concentrations are given in Appendix B.

12.2 Derived and Transformed Data

Baseline will be considered to be the latest value obtained before study drug administration. (e.g. Day 0, pre-dose; or Day -1 if not recorded pre-dose; or Day -2 if not recorded elsewhere etc.)

Laboratory data will be reported in standard units. Out-of-range laboratory tests may be repeated. If a test is out-of-range at a baseline time point and repeated before dosing, the latest repeat value before dosing will be used as baseline. However, if a test is out-of-range and repeated at any other time during the study, the out-of-range value (not the repeat value) will be included in statistical summaries.

Triplicate ECG measurements will be taken at -24 h on Day -1, and at pre dose on Days 0 and 9. The mean of the three measurements taken on Day 0 pre dose for each subject will be used as their baseline value. Single measurements will be made at all other time points.

The pharmacokinetic parameters to be derived are given in Appendix B.

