4.2.2 Secondary Endpoint(s)

Pharmacokinetic Variables:

Emodepside plasma concentration–time data will be used to derive the following PK parameters of emodepside:

- After the first dose of emodepside (Day 0):

- Main PK parameters:
- Cohorts 1 & 2: AUC_{24} , AUC_{24}/D , C_{max} , C_{max}/D
- Cohort 3: AUC_{12} , AUC_{12}/D , C_{max} , C_{max}/D
- After multiple doses of emodepside (Day 9):
 - Main PK parameters:
 - Cohorts 1 & 2: AUC_{∞} , AUC_{∞}/D , AUC_{24} , AUC_{24}/D , $C_{max,ss}$, $C_{max,ss}/D$
 - Cohort 3: AUC_{∞} , AUC_{∞}/D , AUC_{12} , AUC_{12}/D , $C_{max,ss}$, $C_{max,ss}/D$
- Accumulation ratios $RA(C_{max})$ and $RA(AUC_{tau})$ will be calculated
- C_{trough} will be derived from the concentration data (Days 1–9).

The above parameters may be calculated for the metabolites of emodepside, as appropriate.

Pharmacodynamic Variables:

- Time-matched profiles of glucose, glucagon, insulin, and cortisol
- Oral glucose tolerance test (OGTT)

Exploratory PK variables:

Emodepside plasma concentration–time data will be used to derive the following PK parameters of emodepside:

- After a single dose of emodepside (Day 0):
 - Cohorts 1 & 2: $AUC_{24,norm}$, $C_{max,norm}$, t_{max} , MRT_{last} , V_z/F
 - Cohorts 3: $AUC_{12,norm}$, $C_{max,norm}$, t_{max} , MRT_{last} , V_z/F
- After multiple doses of emodepside (Day 9):
 - $AUC_{\infty,norm}$, $AUC_{12,norm}$, $AUC_{24,norm}$, AUC_{last} , AUC_{last}/D , $AUC_{last,norm}$, $C_{max,ss,norm}$, $t_{1/2}$, λ_z , t_{max} , MRT_{∞} , V_z/F , CL_{ss}/F
 - Other optional parameters: AUC_{t-inf} , $\%AUC_{extra}$, points terminal

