4.3 Statistical Hypotheses

Except for the analysis of pharmacokinetic data, no formal statistical testing will be done.

5 Study Design

This will be a single-centre, single-blind, randomized, placebo-controlled, parallel-group, multiple-dose, dose-escalation study.

Each cohort will comprise 8 healthy Caucasian male subjects, 6 of whom will be randomised to receive emodepside, and 2 of whom will be randomised to receive placebo. 3 cohorts will be recruited, to test 3 multiple dose levels of emodepside LSF oral solution over 10 days.

5. Ophthalmological examination will be performed at the second screening visit after all other eligibility criteria have been met, and on Day 10. If deemed necessary by the ophthalmologist, additional ophthalmology follow-up visit(s) may be scheduled for eye-related AEs. Subjects will be given the Ishihara test at screening visit 1.
6. Blood samples taken for glucose and insulin measurement will be used to complete an Oral Glucose Tolerance Test (OGTT). Samples taken will be:
 - on Day -2: at -48, -47, -46 and -44 h before the morning dose on Day 0
 - on Day 1: before and at 1, 2 and 4 h after the morning dose
 - on Day 8: before and at 1, 2 and 4 h after the morning dose
 - On day 120 at 0, 1, 2 and 4 h time points relative to dosingSubjects will fast until completion of the OGTT test; lunch will be provided immediately afterwards
7. Blood samples for measurement of glucose, insulin, glucagon and cortisol will be taken:
 - on Day -1: at -24, -23, -22, -20 and -12 h before the morning dose on Day 0
 - on Day 0: before and at 1, 2, 4 and 12 h after the morning dose
 - on Day 1: before the morning dose
 - on Day 9: before and at the following time points after the morning dose: 1, 2, 4, 12, 24 (Day 10), 48 (Day 11), 72 (Day 12), 96 (Day 13) and 120 h (Day 14); and at follow up (Day 30 (\pm 2 days)). Subjects will fast for the Day 11, 12, 13, 14 and 30 time points.Leptin and prolactin will also be measured at Screening Visit 1 and Day 9, as part of the insulin blood sample.
8. Administration of the study medicine will be done in fasting conditions on Days 0-9 at approximately the same time each morning (\pm 15 mins):
 - in Cohorts 1 & 2, emodepside will be giving in the morning only
 - in Cohort 3, emodepside will be given in the morning and evening (at 12 h intervals). On the last day (day 9), emodepside will be given only in the morning

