15.2 Urinary PK

If concentrations of emodepside and metabolites (if applicable) in urine are determined, the amount of emodepside excreted in the urine will be estimated and listed.

16 Pharmacodynamic Analyses

Summaries and listings will use the safety population.

Pharmacodynamic variables (glucose, insulin, glucagon, cortisol and oral glucose tolerance test) at each planned assessment, and change from baseline at each planned post-baseline assessment, will be summarised by treatment.

Individual PD subject profiles plotted against time will be presented for both absolute values and change from baseline.

17 References

1. International Conference on Harmonization, 1998. Statistical Principles for Clinical Trials - ICH Harmonised Tripartite Guideline. Guidance for Industry, E9, FDA federal register, Vol 63, 1998, p49583. Available at: <http://www.fda.gov/cder/guidance>.
2. International Conference on Harmonization, 1995. Structure and Content of Clinical Study Reports - ICH Harmonised Tripartite Guideline. Guidance for Industry, E3, FDA federal register, Vol 61, 1996, p37320. Available at: <http://www.fda.gov/cder/guidance>.
3. International Conference on Harmonisation, 2005. Clinical Evaluation of QT/QTc Interval Prolongation and Proarrhythmic Potential for Non-Antiarrhythmic Drugs. Concept paper, Guidance for Industry, E14, Center for Drug Evaluation and Research (CDER). Available at: <http://www.fda.gov/cder/guidance/6922fnl.htm>.
4. Julious, SA & Debnarot, CAM (2000) "Why are Pharmacokinetic Data Summarised by Arithmetic Means?", *Journal of Biopharmaceutical Statistics*, 10 (1), p55-71

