System Organ Class	Preferred Term	Treatment 1 (N=xx) n (%)	Treatment 2 (N=xx) n (%)	Etc
Number of subjects with AEs		x (xx.x)	x (xx.x)	
Gastrointestinal disorders	Abdominal discomfort	x (xx.x)	x (xx.x)	
	Abdominal pain	x (xx.x)	x (xx.x)	
	↓			
Nervous system disorders	Dizziness			
	Headache			
	↓			
↓	↓			

n = number of subjects (subjects with ≥1 adverse event are counted only once per system organ class and preferred term)

Based on MedDRA version xx.x

Source: Listing 16.2.xx

*Programming notes: Each preferred term counted only once across all severities for each subject/treatment
 Continued with all treatment groups
 SOCs and PTs are sorted in decreasing order of frequency
 Presented for all applicable MedDRA system organ classes and terms.*

Template T_LB1

Table 14.3.4.xx Summary of laboratory values of potential clinical importance

Laboratory Test (units)	Treatment	Planned Relative		Double Flags	
		Time	n	HI	LD
Treatment 1 (N=xx)					

H = Above reference interval, L = Below reference interval, I = Increase from baseline greater than pre-defined limit, D = Decrease from baseline greater than pre-defined limit

Source: Listing 16.2.xx

Programming notes: Continued with all tests, treatment groups and time points. n = total number of results for that parameter

Template T_LB2

Table 14.3.5.xx Summary of chemistry laboratory values

Laboratory Test (units)	Treatment	Planned Relative Time	n	Mean	SD	Median	Min	Max	n	Change from Baseline					
										Mean	SD	Median	Min	Max	
Treatment 1 (N=xx)															

Source: Listing 16.2.xx

Programming notes: Continued with all treatments and time points

Template T_UR1

Table 14.3.5.xx Summary of urinalysis results

Laboratory Test	Planned Relative Time	Result	Treatment 1 (N=xx)		Treatment 2 (N=xx)	
			n	%	n	%
Time 1		Positive	X	x		
		Negative	X	X		
		Not Done	x			
Time 2		Positive				
		Negative				
		Not Done				

Source: Listing 16.2.xx

Programming notes: Results recorded as received, e.g. Negative, Trace, etc; urine pH summarised as <5, 5-8, >8; specific gravity summarised as <=1.005, 1.006 - 1.010, 1.011 - 1.015, 1.016 - 1.020, 1.021 - 1.025, 1.026 - 1.029, >=1.030. Continued with all treatment groups and time points. The n's sum to N but the calculated percentages exclude Not Done.

Template T_VS1

Table 14.3.6.xx Summary of vital signs

Variable (units)	Treatment	Planned Relative Time	n	Mean	SD	Median	Min	Max	Change from Baseline					
									n	Mean	SD	Median	Min	Max

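### One latest-pre-dose baseline takes 8 of 16 profile changes across clock time and leaves the OGTT baseline unsettled

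*SAP*

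**What the plan says.** - **Baseline.** SAP 12.2: "Baseline will be considered to be the latest value obtained before study drug administration". Its examples start with Day 0 pre-dose, then Day -1, and end with "or Day -2 if not recorded elsewhere etc". ECG has its own baseline rule in the same section; the pharmacodynamic (PD) variables have none.
- **Use.** SAP 16 names the four analytes and the OGTT as PD variables. It summarises their values at each planned assessment, "and change from baseline at each planned post-baseline assessment, will be summarised by treatment". It adds: "Individual PD subject profiles plotted against time will be presented for both absolute values and change from baseline". In SAP 18.1 the PD and OGTT tables all use shell T_LB2, which has one "Change from Baseline" block.
- **Endpoint.** SAP 4.2.2: "Time-matched profiles of glucose, glucagon, insulin, and cortisol".
- **Day -1.** Footnote 7 of the SAP schedule takes profile samples "on Day -1: at -24, -23, -22, -20 and -12 h before the morning dose on Day 0". Protocol 8.3.5 describes the Day -1 procedures as matched in time to Day 0.
- **OGTT.** Footnote 6 takes samples "on Day -2: at -48, -47, -46 and -44 h before the morning dose on Day 0", then four samples on each of Days 1, 8 and 120. By Protocol 8.3.4, 8.3.7 and 8.3.10 the glucose drink follows the first sample on all four days. The Day 120 times are expressed in relation to a dose, although none is given that day.
- **Protocol baseline.** Protocol 8.3 uses a different reference: the last assessment before randomisation.

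**The concern.** The endpoint is a set of time-matched profiles, and the protocol draws a Day -1 profile at the matching clock times. Yet the only planned change refers every sample to one early-morning value. A change at 1, 2, 4 or 12 h then mixes the drug effect with ordinary within-day movement. Protocol 1.4 reports that in the single-dose study the fall in insulin and rise in glucose occurred mostly within 4 h of dosing. Six of the eight affected points fall in that window.

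The OGTT problem is more basic. A post-load value compared with a fasting value, or a fasting value with a post-load one, largely shows the glucose drink. Because the SAP does not settle which sample is the baseline, two programmers could follow it and produce different tables.

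**Working it through.** **1. Check the schedule.** SAP footnote 7 gives Day -1 (5), Day 0 (5), Day 1 pre-dose (1), Day 9 pre-dose to 120 h (10) and Day 30 (1). 5 + 5 + 1 + 10 + 1 = 22, which equals the 22 glucagon tests in the blood-volume table of Protocol 8.4.4.

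**2. Class the profile changes.** Removing the five Day -1 samples and the Day 0 pre-dose sample leaves 22 - 6 = 16.

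| Samples | Number | Same clock time as Day 0 pre-dose |
|---|---|---|
| Day 0: 1, 2, 4, 12 h | 4 | No |
| Day 1 pre-dose | 1 | Yes |
| Day 9 pre-dose | 1 | Yes |
| Day 9: 1, 2, 4, 12 h | 4 | No |
| 24, 48, 72, 96, 120 h after the Day 9 dose | 5 | Yes |
| Day 30 | 1 | Only if a morning visit (assumption) |

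Off-clock: 4 + 4 = 8 of 16, or 9 of 16 if Day 30 is not a morning visit. Six of the eight (1, 2 and 4 h on two days) are fasted with a gap of 1 to 4 h. The other two have a 12 h gap.

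**3. Fallback.** If Day 0 pre-dose is missing, the latest earlier value is the -12 h evening sample on Day -1. Only the two 12 h samples share that clock time, so 16 - 2 = 14 of 16 changes cross it. With -24 h as fallback the count stays at 8.

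**4. OGTT.** Post-baseline values per analyte: 4 times x 3 days (1, 8, 120) = 12. The rule has two literal readings:
- If the OGTT is its own variable, the latest pre-dose value is -44 h, which is 4 h after the drink.
- If glucose and insulin are the variables, it is the Day 0 pre-dose sample, fasting and without a drink.

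The first matches only the 4 h values and the second only the 0 h values, 3 of 12 each. So 12 - 3 = 9 of 12 compare different load states. A fixed -48 h baseline also gives 9. Matching 0, 1, 2 and 4 h to -48, -47, -46 and -44 h gives 0 of 12.

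**5. What the rule does to the treatment comparison.** For a subject at profile time t:

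(value at t - Day 0 pre-dose) - (value at t - Day -1 value at the same clock time) = Day -1 value at that clock time - Day 0 pre-dose value = D.

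D uses pre-dose values only. Under randomisation within a cohort its expectation is the same for active and placebo, so it drops out of the expected active-minus-placebo difference. What remains is chance imbalance. With 6 active and 2 placebo subjects its standard error is SD(D) x sqrt(1/6 + 1/2) = 0.82 x SD(D). The documents do not give SD(D). The OGTT argument is the same, because every candidate baseline is a pre-dose value.

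**The case against.** The strongest reply is that SAP 10 makes active versus placebo the comparison of interest. Placebo subjects are randomised and sampled at the same nominal times, the PD analysis is descriptive, and absolute values are summarised and plotted. The endpoint wording asks for time-matched profiles, not time-matched changes, and the absolute displays provide those. Matching to Day -1 also exchanges within-day variation for day-to-day variation, and nothing in the documents shows which is larger.

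Most of this stands, and it rules out several stronger readings that a reader might infer:

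- *The PD comparison is biased.* Step 5 shows that it is not, in expectation.
- *The Day -1 data are wasted.* They are summarised and plotted as absolute values, and they enter change as the fallback.
- *Half of all PD changes are off-clock.* The 8 of 16 applies to the four-analyte profile only; the OGTT is counted separately.
- *The OGTT baseline is a Day -2 value and only its time is unclear.* The Day 0 pre-dose sample is an equally literal reading.
- *All 16 points should move to Day -1.* Seven already match Day 0 pre-dose, which is a valid and more recent baseline for them.

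The reply does not settle the OGTT baseline. Nor does it supply the within-subject matched change. With complete pairs the absolute tables give its mean by subtraction, but not its SD, median or range. The placebo reference is also thin: Cohort 3 is tabulated separately, with 2 planned placebo subjects.

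**Conclusion.** The concern holds in a limited form. For the four-analyte profile, 8 of 16 changes cross clock time (assuming a morning Day 30 visit), and the literal fallback would raise this to 14 of 16. For the OGTT, the SAP does not fix the baseline sample, and any single value leaves 9 of 12 changes per analyte comparing different glucose-load states. The OGTT gap is the more serious part, because the planned change table cannot be read as written.

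The consequence is imprecision and poor interpretability of change within an arm. The documents do not support a claim of bias in active versus placebo, and they give no figure from which to size the effect in concentration units. The counts rest on nominal times. The Day 1 and Day 8 OGTT samples are scheduled from the dose and the interval from drink to dose is not stated, so that match is nominal as well.

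**What to change.** Before Cohorts 1 and 2 are unblinded, amend SAP 12.2 and 16:

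- **(a) OGTT.** Define baseline as the same subject's Day -2 value at the same nominal OGTT time: -48, -47, -46 and -44 h for 0, 1, 2 and 4 h. Define 0 h as the sample before the drink, on Day 120 as well.
- **(b) Profiles.** Keep change from Day 0 pre-dose. Add a prespecified within-subject time-matched change for 1, 2, 4 and 12 h on Days 0 and 9, against Day -1 at -23, -22, -20 and -12 h. Footnote that Day -1 has no dose administration and that the 12 h pair is not shown to be meal-matched.
- **(c) Fallback.** If Day 0 pre-dose is missing, use the Day -1 value at -24 h for the profiles, not the latest value.
- **(d) Definition.** Reconcile SAP 12.2 with Protocol 8.3. The two may agree in practice, since Protocol 6 links being randomised to the first dose, but the wording differs.

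The cost is SAP wording, slightly more programming and one extra display. All samples are already scheduled and no endpoint is added. Timing matters because, under SAP 3, analyses added after database lock do not enter an amended SAP and are reported as unplanned.

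Separately, Protocol 4.3 and 7.1 place a Cohort 3 evening dose on Days 0 to 9, while Protocol 8.3.8 has a morning dose only on Day 9. These sections conflict and must be reconciled.

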12.3 Assessment Windows

No assessment windows are defined for this report.

12.4 Values of Potential Clinical Importance

Any laboratory value outside the reference interval for that variable will be flagged with an 'H' if it is higher than the reference interval, and with an 'L' if it is lower. Additionally, if, during the course of the trial, a variable changes from baseline (Day 0 pre dose) by more than a predetermined amount (as defined by the Principal Investigator, Appendix A), that value will receive a flag 'I' if increased, or 'D' if decreased. Therefore, if a value both falls outside the reference interval and alters from the baseline value by more than the predetermined amount, it will attract a double flag and will be considered to be potentially clinically important.

A vital signs result will be considered to be of potential clinical importance if it falls outside the relevant range below:

Vital Sign	Range
Supine/semi-recumbent systolic blood pressure	85–160 mm Hg
Supine/semi-recumbent diastolic blood pressure	40–90 mm Hg
Supine/semi-recumbent heart rate	35–100 beats/min
Respiration rate	8–20 per min
Oral temperature	35.5–37.8°C

QT, QTcB or QTcF > 450 msec and increases in QT, QTcB or QTcF from baseline of > 30 msec will be considered to be potentially clinically important.

13 Study Population

